10.2.2 Incidence of Adverse Events

The summaries will include the total number of subjects reporting an AE, the percentage of subjects (%) with an AE, and the number of events (E) reported. AEs will be presented by SOC sorted alphabetically and PT sorted in decreasing frequency of occurrence.

Summary tables will be prepared for:

- Any TEAEs
- Common TEAEs, defined as TEAEs with an incidence $\geq 2\%$ of subjects in any treatment group
- Any TEAEs by causality (related/unrelated)
- Any TEAEs by intensity
- Any AEs leading to death
- Serious adverse events
- Any TEAEs leading to discontinuation

Supporting data listings will be provided for:

- All adverse events sorted by trial site and subject ID
- All adverse events sorted by MedDRA SOC and PT
- Serious adverse events
- Adverse events leading to death
- Adverse events leading to discontinuation

A listing of SOC and PT for all unique verbatim will be provided.

For the open-label period, the following summaries and listings will be provided for subjects who receive the open-label treatment:

- Any TEAEs
- Any TEAEs by causality (related/unrelated)
- Any TEAEs by intensity
- Any AEs leading to death
- Serious adverse events
- Any TEAEs leading to discontinuation

10.3 Safety Laboratory Variables

Baseline for all laboratory analyses will be the values obtained at the last assessment prior to the first dose of the IMP. Treatment-emergent laboratory data will include tests completed after the first dose of IMP. End of double-blind period will include the last post-baseline observation during the double-blind period. End of open-label period will include the last observation during the open-label period.

Laboratory variables will be grouped under “Haematology”, “Coagulation”, “Serum chemistry” or “Urinalysis”

10.3.1 Summary Statistics

Change and percentage change from baseline at end of double-blind period will be presented for each laboratory variable. In addition, descriptive statistics, i.e., the number of subjects with data,

mean (standard deviation), median, minimum, and maximum values, will be presented for observed values and change/percentage change from baseline at baseline, Weeks 2, and 8 for each laboratory variable. The Weeks 2 and 8 measurements for the analysis will be identified based on the method described in Section 9.1.

For the open-label period, similar summaries will be provided for subjects who receive the open-label treatment.

10.3.2 Laboratory Variable Changes Relative to Normal Range

A shift table regarding the laboratory value category defined below will be created for baseline and end of double-blind period for each laboratory parameter.

- Low: Values which are below the lower reference range limit;
- Normal: Values which are within the lower and upper reference range;
- High: Values which are above the upper reference range limit.
- Absent: No value for measured variable (for urinalysis only)
- Present: Any value obtained for measured variable (for urinalysis only)

For the open-label period, similar shift tables will be provided for subjects who receive the open-label treatment.

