## **7.1.7 Clinical Laboratory Variables**

### **Hematology, Serum Chemistry, and Urinalysis**

Safety hematology, coagulation, and serum chemistry tests will be performed at Visit 0 (screening), Visits 4 and 5 (Week 8) or at early withdrawal during the double-blind treatment period, Visit 6 (Week 10) and Visits 7 and 8 (Week 16) during the open-label treatment period.

Hematology: hematocrit, hemoglobin, platelet count, red blood cell count, white blood cell count, and differential count

Coagulation: prothrombin time (measured as international normalized ratio), activated partial thromboplastin time

Serum chemistry: glucose, blood urea nitrogen, creatinine, creatinine clearance (via estimated glomerular filtration rate [eGFR]), potassium, sodium, chloride, calcium, total protein, albumin, total bilirubin, alkaline phosphatase, aspartate aminotransferase, alanine aminotransferase, and gamma glutamyl transferase

Urinalysis: leukocyte, blood, pH, specific gravity, nitrite, protein, glucose, urobilinogen, and microscopic if positive for blood, leucocytes, and nitrite

The investigator will review the laboratory results and evaluate and document whether the results are normal or abnormal and whether abnormal results are clinically significant. The laboratory report will be signed and dated by the investigator.

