10.3.3 Markedly Abnormal Changes

Number and percentage of subjects who experienced at least one pre-specified markedly abnormal value ([Appendix 1](#)) during the double-blind period for each laboratory variable will be summarized by the baseline category defined in Section 10.3.2 (i.e., low, normal, high, absent, or present).

For the open-label period, similar summaries will be provided for subjects who receive the open-label treatment.

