Appendix 1 Markedly Abnormal Laboratory Safety Values, Vital Signs and ECGs

Table A 1. Markedly abnormal Criteria for Laboratory Tests

Variable	Units	Markedly abnormal Criteria	
		Low	High
Haematology			
Haemoglobin	g/L	≤ 115	Not applicable
Haematocrit	Ratio	≤ 0.32	≥ 0.56
Total WBC	10 ⁹ /L	≤ 2.8	≥ 16.0
Eosinophils	%	Not applicable	≥ 10
Neutrophils	%	≤ 15	≥ 90
Lymphocytes	%	≤ 10	≥ 80
Monocytes	%	Not applicable	≥ 20
Basophils	%	Not applicable	≥ 5
Platelets	10 ⁹ /L	≤ 75	≥ 700
Total RBC	10 ¹² /L	≤ 3.5	Not applicable
Clinical Chemistry			
AST	IU/L	Not applicable	> 3xULN
ALT	IU/L	Not applicable	> 3xULN
Alkaline phosphatase	IU/L	Not applicable	> 3xULN and 25% increase from baseline
GGT	IU/L	Not applicable	> 3xULN
Total bilirubin	µmol/L	Not applicable	≥ 1.5xULN
Urea nitrogen	mmol/L	Not applicable	≥ 10.7
Creatinine	µmol/L	Not applicable	≥ 177
eGFR	mL/min	<30	Not applicable
Total protein	g/L	≤ 45	≥ 90
Albumin	g/L	≤ 25	≥ 65
Sodium	mmol/L	≤ 130	≥ 155
Potassium	mmol/L	≤ 3.0	≥ 5.8
Chloride	mmol/L	≤ 90	≥ 115
Calcium	mmol/L	≤ 1.8	≥ 3.9
Glucose	mmol/L	≤ 2.8	≥ 10
Coagulation			
INR		<0.8	>1.1
Activated partial thromboplastin time	Sec	Not applicable	>70

Table A 2. Markedly abnormal Criteria for Vital Signs*

Variable	Criterion Value	Change from Baseline
Systolic blood pressure	≥ 180 mmHg	Increase of ≥ 20 mmHg
	≤ 90 mmHg	Decrease of ≥ 20 mmHg
Diastolic blood pressure	≥ 105 mmHg	Increase of ≥ 15 mmHg
	≤ 50 mmHg	Decrease of ≥ 15 mmHg
Pulse rate	≥ 120 bpm	Increase of ≥ 15 bpm
	≤ 50 bpm	Decrease of ≥ 15 bpm
Body temperature		Increase to ≥ 39.4°C

* To be identified as markedly abnormal, a treatment value must meet the criterion value and also the specified change from baseline.

Table A 3. Abnormal Criteria for Quantitative ECG Data*

Variable	Abnormal Treatment-Emergent Value
ECG heart rate	≤ 50 bpm and decrease from baseline of ≥ 15 bpm ≥ 120 bpm and increase from baseline of ≥ 15 bpm
Duration of PR interval	> 220 msec
Duration of QRS interval	> 120 msec
Duration of QTc interval	> 450 msec
Duration of QTc interval	> 480 msec
Duration of QTc interval	> 500 msec
Duration of QTc interval	Increase from baseline of ≥ 30 msec
Duration of QTc interval	Increase from baseline of ≥ 60 msec

* QTc will be calculated using both Bazett's and Fridericia's corrections.

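### SAP 10.3.2 defines the urinalysis shift categories by whether a value exists, not by whether the analyte was detected, so as written the Absent/Present table cannot show new urinary findings

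*SAP*

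**What the plan says.** SAP 10.3.2 plans a shift table that "will be created for baseline and end of double-blind period for each laboratory parameter", with similar tables for the open-label period. Three categories depend on a reference range; for example, "High: Values which are above the upper reference range limit". Two more are reserved for urinalysis: "Absent: No value for measured variable (for urinalysis only") and "Present: Any value obtained for measured variable (for urinalysis only"). No category for missing results is given.

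SAP 10.3.3 then counts subjects with at least one pre-specified markedly abnormal value for each laboratory variable, "summarized by the baseline category defined in Section 10.3.2 (i.e., low, normal, high, absent, or present"). The criteria are in SAP Appendix 1, Table A 1, titled "Markedly abnormal Criteria for Laboratory Tests".

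Protocol 7.1.7 sets the panel: "Urinalysis: leukocyte, blood, pH, specific gravity, nitrite, protein, glucose, urobilinogen, and microscopic if positive for blood, leucocytes, and nitrite". Protocol Table 1 schedules urinalysis at Visits 0, 2, 5, 6 and 8.

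**The concern.** A shift table for a dipstick analyte should show who went from not detected to detected. The two urinalysis definitions do not mention detection. On their plain words a negative result is a value obtained and counts as Present, while Absent is left for a subject with no result. The table then separates results from missing results and hides the change it exists to show.

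The incidence of abnormal laboratory values is part of a listed secondary endpoint (Protocol 2.2, SAP 2.2.3). Protocol 9.8.3 also promises the number and percentage of subjects with treatment-emergent, potentially clinically significant laboratory values. If the definitions are programmed as written, the laboratory tables may give no comparison between arms of new urinary protein, blood, leukocytes or nitrite.

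**Working it through.** The plan states no figure here, so the check applies the definitions to every possible pair of results and then looks for other outputs that would count a new finding.

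**Step 1. Apply the rule.** As written, Absent means no value and Present means any value. The comparison rule is Absent = tested and not detected, Present = detected, with missing kept separate.

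| Baseline to end | As written | Detection-based |
|---|---|---|
| negative to negative | Present to Present | Absent to Absent |
| negative to positive | Present to Present | Absent to Present |
| positive to negative | Present to Present | Present to Absent |
| positive to positive | Present to Present | Present to Present |
| negative to missing | Present to Absent | Absent to missing |
| positive to missing | Present to Absent | Present to missing |
| missing to negative | Absent to Present | missing to Absent |
| missing to positive | Absent to Present | missing to Present |
| missing to missing | Absent to Absent | missing to missing |

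All four pairs with two results fall in one cell under the written rule. Off-diagonal cells arise only from missing results.

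**Step 2. Size, as an illustration.** Assume an arm of 110 (the planned number per group), all tested and negative at baseline and all tested at the end, with k new positives. The value of k is an assumption; the documents give no rate.

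| k | k/110 | Absent-to-Present, as written | Absent-to-Present, detection-based |
|---|---|---|---|
| 0 | 0% | 0 | 0 |
| 5 | 4.5% | 0 | 5 |
| 11 | 10% | 0 | 11 |
| 22 | 20% | 0 | 22 |

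The written rule returns 0 whatever k is.

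**Step 3. The markedly abnormal table.** Table A 1 has 10 haematology rows, 15 clinical chemistry rows and 2 coagulation rows: 10 + 15 + 2 = 27, with 0 for urinalysis. Its total protein and glucose rows belong to the clinical chemistry block. SAP 10.3.3 therefore names two urinalysis-only strata for a table that has no urinalysis criterion to count.

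**Step 4. Other outputs.**
- SAP 10.3.1 gives means, medians and ranges for each laboratory variable. These do not count new positives.
- Low/Normal/High in 10.3.2 is not barred for urinalysis. It could classify an analyte if the laboratory supplies a reference range, but the documents do not say for which urinalysis variables it does.
- SAP 10.3.4 lists, by treatment group and site, all subjects with any abnormal laboratory value. This is a listing, not a count.
- Protocol 8.1 makes a laboratory abnormality an AE if the investigator judges it clinically significant, and SAP 10.2.2 tabulates TEAEs with numbers and percentages. Protocol 7.1.6 leaves the reporting of laboratory abnormalities as AEs to the investigator's discretion.

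**The case against.** The strongest reply is that the literal reading is not what the author meant. The section concerns change relative to the normal range, and blood, protein and nitrite are naturally detected or not detected, so value may have been meant as a positive reading. The table shells are in a separate document (SAP 14), so the programming cannot be known. This stands in part: the documents show a wording defect, not a programmed error. But the kinder reading does not repair the text. Tested-negative and not-tested would then both be Absent, and pH and specific gravity, which have a value whenever tested, would not fit.

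Four stronger inferences are tempting, and the documents do not support them.
- *New urinary findings are counted nowhere.* The TEAE tables count those judged clinically significant, and the listing shows every abnormal value.
- *pH and specific gravity will always be Present.* Low/Normal/High is open to them. The SAP only fails to say which scheme applies.
- *Missing samples will create false shifts.* This should be rare. Screening urinalysis results must be available at randomization (Protocol Table 1, note b), and SAP 10.3 takes the last post-baseline observation as the end of the double-blind period. With urinalysis at Visits 2 and 5, a subject without a Visit 5 result can still contribute the one from Visit 2.
- *Renal safety goes uncounted.* Table A 1 has criteria for creatinine, urea nitrogen and eGFR.

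It is also fair to say that SAP 10.3.3 counts only pre-specified values, and that setting no dipstick threshold is the sponsor's choice. The remaining fault there is that two strata are announced with nothing to fill them.

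**Conclusion.** The point holds as a defect of definition. Taken as written, the Absent/Present shift table cannot show a new urinary finding at any rate of occurrence, and missing results have no category of their own. Since missing results should be few, that table would be almost wholly Present-to-Present. Because Table A 1 has no urinalysis criterion, no laboratory summary table is sure to count new urinary protein, blood, leukocytes or nitrite by arm. The subject listing and, at the investigator's judgement, the TEAE tables remain.

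A reader might go further and conclude that the reported table will merely show who gave a urine sample. That depends on programming the documents do not disclose.

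Severity is minor. The tables are descriptive safety outputs, and the efficacy analyses are unaffected. The illustrative counts assume 110 subjects per arm with complete results; the conclusion does not depend on them.

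**What to change.** In SAP 10.3.2:
- define Absent as tested and not detected;
- define Present as detected at a stated grade (for example, trace or above);
- show missing as a separate category;
- state that urinalysis variables with a reference range, such as pH and specific gravity, use Low/Normal/High, and that the others use Absent/Present.

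In SAP 10.3.3 and Table A 1, choose one of two courses. Either add urinalysis criteria, or state that none are set and delete the Absent and Present strata from 10.3.3. Both are acceptable; graded criteria are optional.

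Apply the same definitions to the open-label tables and check the shells against them. The cost is a few lines of SAP text and a matching change to the shells, with no new data.

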10.3.3 Markedly Abnormal Changes

Number and percentage of subjects who experienced at least one pre-specified markedly abnormal value ([Appendix 1](#)) during the double-blind period for each laboratory variable will be summarized by the baseline category defined in Section 10.3.2 (i.e., low, normal, high, absent, or present).

For the open-label period, similar summaries will be provided for subjects who receive the open-label treatment.

10.3.4 Data Listings

Data listings will be prepared by treatment group and trial site for all subjects with any abnormal laboratory values at any time-point (including screening, baseline, double-blind period, and open-label period).

10.4 Vital Signs and ECG

10.4.1 Vital Signs

Baseline for all vital signs will be the values obtained at the last assessment prior to the first dose of IMP. Treatment-emergent vital signs data will include tests completed after the first dose of IMP. End of double-blind period will include the last post-baseline observation during the double-blind period. End of open-label period will include the last observation during the open-label period.

10.4.1.1 Summary Statistics

Change and percentage change from baseline at end of double-blind period will be presented for each vital sign variable. In addition, descriptive statistics, i.e., the number of subjects with data, mean (standard deviation), median, minimum, and maximum values, will be presented for observed values and change/percentage change from baseline at baseline, Weeks 2, 4, and 8 for each vital sign variable. The Weeks 2, 4, and 8 measurements for the analysis will be identified based on the method described in Section 9.1.

For the open-label period, similar summaries will be provided for subjects who receive the open-label treatment.

10.4.1.2 Markedly Abnormal Changes

Number and percentage of subjects who experienced at least one pre-specified markedly abnormal value ([Appendix 1](#)) during the double-blind period for each vital sign variable will be summarized.

For the open-label period, similar summaries will be provided for subjects who receive the open-label treatment.

10.4.1.3 Data Listings

Data listings will be prepared by trial site for all subjects with any markedly abnormal vital sign values at any time-point (including screening, baseline, double-blind period, and open-label period).

10.4.2 ECGs

Baseline for all ECG variables will be the values obtained at the last assessment prior to the first dose of IMP. Treatment-emergent ECG data will include values measured after the first dose of IMP. End of double-blind period will include the last post-baseline observation during the double-blind period. End of open-label period will include the last observation during the open-label period.

QTc will be calculated based on Bazett's (QTcB) and Fridericia's (QTcF) corrections.

$$QTcB[ms] = \frac{QT}{\sqrt{RR}}$$

$$QTcF[ms] = \frac{QT}{\sqrt[3]{RR}}$$

$$\text{where, } RR = \frac{60}{\text{Heart Rate}}$$

10.4.2.1 Summary Statistics

Change from baseline at end of double-blind period will be presented for each ECG variable. In addition, descriptive statistics, i.e., the number of subjects with data, mean (standard deviation), median, minimum, and maximum values, will be presented for observed values and change from baseline at baseline and Week 8 for each ECG variable. The Week 8 measurement for the analysis will be identified based on the method described in Section 9.1.

For the open-label period, similar summaries will be provided for subjects who receive the open-label treatment.

10.4.2.2 Markedly Abnormal Changes

Number and percentage of subjects who experienced at least one pre-specified markedly abnormal value ([Appendix 1](#)) during the double-blind period for each ECG variable will be summarized.

For the open-label period, similar summaries will be provided for subjects who receive the open-label treatment.

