### **STATISTICAL METHODS (Continued)**

**Safety:** The safety analyses will be based on all subjects who receive at least 1 dose of IMP. All adverse events will be coded by system organ class and preferred term using the most current version of the Medical Dictionary for Regulatory Activities (MedDRA). A treatment-emergent adverse event will be defined as any adverse event occurring after the start of IMP or pre-existing medical condition that worsens in intensity after the start of IMP.

Clinical laboratory variables will be presented in 2 ways. First, mean change from baseline to the end of the double-blind treatment visit will be summarized. Baseline will be defined as the last assessment before the first dose of IMP. Second, the number and percentage of subjects with treatment-emergent potentially clinically significant laboratory values on or before the end of the double-blind treatment visit will be tabulated.

Other safety assessments will also be summarized descriptively.

Similar safety data summaries will be made for the open-label treatment period data.

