### **9.8.3 Safety Laboratory Variables**

Clinical laboratory variables will be presented in 2 ways. First, mean change from baseline to the end of the double-blind treatment visit will be summarized. Baseline will be defined as the last assessment before the first dose of IMP. Second, the number and percentage of subjects with treatment-emergent

potentially clinically significant laboratory values on or before the end of the double-blind treatment visit will be tabulated.

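### The ECG counts for PR, QRS and absolute QTc limits are labelled treatment-emergent but include subjects already past the limit before dosing; a smaller version of this gap remains in the laboratory counts

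*SAP*

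**What the plan says.** **ECG.** SAP 10.4.2 sets the scope: "Treatment-emergent ECG data will include values measured after the first dose of IMP". SAP 10.4.2.2 then gives, for each ECG variable, the "Number and percentage of subjects who experienced at least one pre-specified markedly abnormal value" in the double-blind period, with a similar summary for the open-label period. The criteria are in Appendix 1, Table A 3, under the column heading "Abnormal Treatment-Emergent Value". They are of two kinds:

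- absolute limits alone: PR >220, QRS >120, and QTc >450, >480 and >500 msec;
- criteria tied to baseline: heart rate ≤50 or ≥120 bpm together with a change of at least 15 bpm, and QTc increases of at least 30 and at least 60 msec.

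**Vital signs.** The footnote to Table A 2 asks for both elements: "To be identified as markedly abnormal, a treatment value must meet the criterion value and also the specified change from baseline".

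**Laboratory.** The protocol synopsis, and Protocol 9.8.3 in the same terms, plan a count of "subjects with treatment-emergent potentially clinically significant laboratory values". SAP 10.3 takes the label to mean timing: "Treatment-emergent laboratory data will include tests completed after the first dose of IMP". SAP 10.3.3 counts markedly abnormal values "during the double-blind period for each laboratory variable will be summarized by the baseline category defined in Section 10.3.2", and 10.3.2 sets those categories by the laboratory reference range. Table A 1 holds the limits, including haemoglobin ≤115 g/L, eGFR <30 mL/min, creatinine ≥177 µmol/L and urea nitrogen ≥10.7 mmol/L. Alkaline phosphatase is its only row with a change condition (25% above baseline).

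**The concern.** A count labelled treatment-emergent is read as a count of things that appeared or worsened on treatment. As the SAP defines the term for ECG and laboratory data, it means only that the value was measured after the first dose. Nothing requires the value to be new.

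For the absolute ECG limits, a stable conduction finding or a stable long QTc recorded at screening therefore becomes an on-treatment event at Week 8. Randomisation should spread such subjects evenly, so the expected effect in the double-blind table is an equal background in both arms. That background leaves the difference in percentages almost unchanged but pulls the ratio towards 1. The open-label table has no concurrent placebo group, so there the background simply raises the apparent event rate.

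The SAP handles the same problem correctly for vital signs, so the gap looks like an inconsistency inside Appendix 1 and not a considered choice.

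**Working it through.** The plan states no figure that depends on this point, so there is nothing to reproduce. The check is a comparison of passages, followed by a sizing on assumed rates.

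**1. Which rules look at baseline?**

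| Table | Criterion uses baseline? | Count split by baseline? |
|---|---|---|
| A 2, vital signs | Yes, limit and change | Not needed |
| A 3, heart rate and QTc increase | Yes | Not needed |
| A 3, PR, QRS, QTc >450/480/500 | No | No (SAP 10.4.2.2) |
| A 1, laboratory | Only alkaline phosphatase | Yes, by reference range (SAP 10.3.3) |

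SAP 10.4.2 plans no ECG shift table.

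**2. Can affected subjects be enrolled?** Yes. None of the 18 exclusion criteria in Protocol 4.1.2 concerns the ECG. Protocol Table 1 schedules an ECG at screening and one at the end of double-blind treatment, so each subject has the pair of values needed to tell old from new.

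**3. Size for the ECG rows.** Inputs: 110 subjects per arm (SAP 3.2), and an assumed fraction q already past a limit and staying there. Expected carry-over cases per arm = 110 × q. Chance of at least one per arm = 1 − (1 − q)^110.

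For the effect on the comparison, also assume new abnormalities in 4% v 1% of subjects not past the limit at baseline. Reported rate = q + (1 − q) × new rate. At q = 5%, for example, this is 0.05 + 0.95 × 0.04 = 8.8% against 0.05 + 0.95 × 0.01 = 6.0%.

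| q | Carry-over per arm | Chance of ≥1 | Reported rates | Ratio | Difference (points) |
|---|---|---|---|---|---|
| 1% | 1.1 | 67% | 5.0% v 2.0% | 2.5 | 2.97 |
| 2% | 2.2 | 89% | 5.9% v 3.0% | 2.0 | 2.94 |
| 5% | 5.5 | 99.6% | 8.8% v 6.0% | 1.5 | 2.85 |
| 10% | 11.0 | >99.9% | 13.6% v 10.9% | 1.25 | 2.70 |

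A count of new cases among subjects not past the limit at baseline would show 4% v 1%, a ratio of 4 and a difference of 3 points, at every q.

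**4. Laboratory rows.** A subject in the normal range at baseline sits in a separate row of the 10.3.3 table. What is left is the low and high rows. Below the reference range is not the same as at or below the markedly abnormal limit, so the low row for haemoglobin combines subjects already at ≤115 g/L with subjects who were low but above 115 g/L and then crossed.

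Some variables are largely protected. ALT or AST ≥3 × ULN is excluded at entry and the flag is >3 × ULN. Entry needs creatinine clearance ≥60 mL/min and the eGFR flag is <30. Alkaline phosphatase has its change condition.

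**5. The eGFR limit against the entry limit.** Protocol 7.1.7 gives creatinine clearance by way of eGFR, so the two are treated as one quantity. For a baseline b ≥60, a halved value is b/2 ≥30, which is never <30. The fall needed to be flagged exceeds 1 − 30/b: 50% from 60, 62.5% from 80, 66.7% from 90, 70% from 100 and 75% from 120.

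**The case against.** Five points can fairly be made for the plan.

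- **The protocol commits to treatment-emergent counts for laboratory values only.** Protocol 9.8.4 asks for other safety assessments to be summarised descriptively. This stands, so the ECG point is not a breach of the protocol. It rests on the SAP's own label in Table A 3.
- **Other ECG outputs look at baseline.** Changes from baseline are summarised for each ECG variable, two QTc rows count increases, and subjects with abnormal ECG findings at any time, screening included, are listed. This stands as mitigation. But PR and QRS have no change row, and neither means nor listings give a count of new cases by arm.
- **The rates in the sizing are assumed and no test is planned on these tables.** This stands. The figures show direction and scale only.
- **Dropping subjects already abnormal would hide those who worsen**, for example haemoglobin from 112 to 80 g/L. This stands, and it is why the fix is a split and not an exclusion.
- **The laboratory table already has a baseline split.** This stands for subjects in the normal range at baseline. A reader might infer that the laboratory counts are as mixed as the ECG counts; SAP 10.3.3 does not support that.

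A reader might also infer from step 5 that a large renal decline would leave no mark in the table. The documents do not support that either. Table A 1 also flags creatinine ≥177 µmol/L and urea nitrogen ≥10.7 mmol/L, and SAP 10.3.1 gives percentage change for every laboratory variable. If eGFR is inversely proportional to creatinine (an assumption), a fall from 90 to 35 mL/min multiplies creatinine by 90/35 = 2.57, so the creatinine row would flag it from a baseline of about 177/2.57 = 69 µmol/L upwards. An exact halving would be flagged from 177/2 = 88.5 µmol/L.

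**Conclusion.** The point holds in full for five ECG criteria: PR >220, QRS >120 and QTc >450, >480 and >500 msec. As written, the SAP counts unchanged pre-dose findings as treatment-emergent in both arms and in the open-label table. With 1% to 10% of subjects already past a limit, that is about 1 to 11 subjects per arm. Under the assumed 4% v 1%, the ratio falls from 4 to between 2.5 and 1.25, while the difference stays near 3 points. The documents give neither the prevalence nor the new-event rates, so only the direction is certain.

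For laboratory values only the mix within the low and high rows remains, with haemoglobin the clearest example. This takes each markedly abnormal limit to lie outside the reference range; the documents print no ranges, so that cannot be checked.

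The eGFR limit and the entry criterion do not fit together: no exact halving is flagged in any subject who meets the entry criterion. The creatinine and urea nitrogen rows and the percentage-change summaries cover part of this, but no output counts subjects by relative fall in eGFR.

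No efficacy conclusion is touched. The point concerns how safety tables will be read, and it should be settled before unblinding.

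**What to change.** 1. In SAP 10.4.2.2, tabulate each absolute-limit criterion (PR, QRS and the three QTc limits) by whether the subject's baseline value already met that same criterion. Do the same within the low and high rows of 10.3.3.
2. Report new cases among subjects who did not meet the criterion at baseline as the treatment-emergent count, with those subjects as the denominator.
3. Show subjects who did meet it at baseline in a separate row with their change from baseline, so that worsening stays visible.
4. Apply the same layout to the open-label tables.
5. Reconcile the eGFR limit in Table A 1 with the renal entry criterion, or state why the two differ. No threshold is proposed here.

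Cost: a few lines of SAP text and one programming condition. Baseline ECG and laboratory values are already collected at screening, so no new data are needed. The downsides are one more row per variable and a smaller denominator for the new-case row: at 5% already past a limit, 110 − 5.5 = 104.5 expected per arm; at 10%, 110 − 11 = 99.
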